#### General Exclusion Criteria

1. Patient with DVT in the target limb of which the onset of symptoms is between 15 days and 6 months prior to planned treatment or patient has an acute DVT anywhere else than in the target vessel;
2. Patient has peripheral arterial disease causing symptoms in target limb;
3. Patient is pregnant (female patients of child-bearing potential must have a pregnancy test done within 7 days prior to the index procedure);
4. Patient has a known or suspected systemic infection at the time of the index procedure;
5. Patient has a planned percutaneous or surgical intervention within 30 days prior or 30 days following index procedure, or a contralateral iliofemoral lesion requiring planned treatment within 12 months;

	
 
6. Patient requires femoral endovenectomy and patch venoplasty, greater saphenous vein ablation, and/or small saphenous vein stripping during the index procedure;
 
7. Patient has an active vasculitic inflammatory disorder (e.g. Behcet disease) predisposing the patient to thrombosis and requiring systemic corticosteroid therapy;
 
8. Patient has impaired renal function (GFR < 30) or is on dialysis;
 
9. Patient has a platelet count < 50,000 cells/mm^3 or > 1,000,000 cells/mm^3 and/or a WBC < 3,000 cells/mm^3 or > 12,500 cells/mm^3;
 
10. Patient has a history of bleeding diathesis or either a history or presence of heparin-induced thrombocytopenia antibodies;
 
11. Patient has a known hypersensitivity or contraindication to antiplatelets or anticoagulation, nitinol, or a contrast sensitivity that cannot be adequately pre-medicated;
 
12. Patient has presence of other severe co-morbid conditions, which in the investigator's opinion may interfere with the patient's compliance with study visits and procedures, or may confound interpretation of study data (e.g. congestive heart failure Class III and IV, non-ambulatory patients, severe hepatic dysfunction, life expectancy < 1 year);
 
13. Patient belongs to a vulnerable population per investigator's judgment or patient has any kind of disorder that compromises his/her ability to give written informed consent and/or to comply with study procedures. Patient must be able to consent for themselves;
 
14. Patient is currently participating in another investigational drug or device study or observational competitive study.
 
 
Imaging-based Exclusion Criteria
 
 
15. Patient has a vena cava obstruction or lesion extending into the inferior vena cava (IVC), or the presence of bilateral iliofemoral venous lesions requiring planned treatment within 12 months;
 
16. Patient has significant venous bleeding, arterial dissection or other injury requiring additional percutaneous or surgical intervention prior to enrollment;
 
17. Patient has a previously placed stent in the ipsilateral venous vasculature;
 
18. Patient has disease that precludes safe advancement of the venous stent to the target lesion(s).
 

--	--

Statistics	
The study is designed to meet performance goals (PG) established via review of the clinical venous stent literature. A 30-day Major Adverse Event PG of 12.5% and a 12-month Primary Patency PG of 75% in patients with venous occlusive disease are used.
 
200 subjects are planned for inclusion. This includes correction for 20% lost-to-follow-up on the effectiveness endpoint and 3.5% lost-to-follow-up on the composite safety endpoint. The sample size is driven by the primary effectiveness and safety endpoints and based on a one-sided alpha of 0.025 and at least 80% overall study power.
 
Primary analyses will be conducted after a minimum of 160 subjects have evaluable primary patency data at 12 months to evaluate the primary effectiveness endpoint and 193 subjects have evaluable follow-up data at 30 days to evaluate the primary safety endpoint.
 
A premarket approval application was submitted to FDA once all available 12-month follow-up data was collected on April 27, 2020.
 
The primary effectiveness endpoint of the post-approval study phase is Target Lesion Revascularization (TLR) through 36 months. The newly added objective will be characterized with descriptive statistics. Time-to-event analysis will be performed for the TLR rate through 36 months (1080 days), subjects with no TLR will be censored at the last contact date. Kaplan-Meier estimate and the 95% confidence interval for the freedom from TLR rate through 36 months will be reported.
																																																						
Study Procedures and Assessments	
Schedule of Assessments and Visit Windows
 
  
 Data Collection Requirement	Screening/Baseline (<30 days before procedure unless otherwise specified)	Procedure	Hospital Discharge	30 Day (-7/+14 days)	6 Months (± 30 days)	12 Months (± 30 days)	24 & 36 Months (± 30 days)	Unscheduled visit for intervention in target vein	
   
 Informed Consent	X								
 
 Demographics, Medical History & Physical Exam	X								
 
 Pregnancy Test	X								
 
 CEAP Classification	X								
 
 Physical Assessment of Limbs	X		X	X	X	X	X	X	
  
	Data Collection Requirement	Screening/Baseline (<30 days before procedure unless otherwise specified)	Procedure	Hospital Discharge	30 Day (-7/+14 days)	6 Months (± 30 days)	12 Months (± 30 days)	24 & 36 Months (± 30 days)	Unscheduled visit for intervention in target vein	Informed Consent	X								Demographics, Medical History & Physical Exam	X								Pregnancy Test 	X								CEAP Classification	X								Physical Assessment of Limbs	X		X	X	X	X	X	X
Data Collection Requirement	Screening/Baseline (<30 days before procedure unless otherwise specified)	Procedure	Hospital Discharge	30 Day (-7/+14 days)	6 Months (± 30 days)	12 Months (± 30 days)	24 & 36 Months (± 30 days)	Unscheduled visit for intervention in target vein																																															
Informed Consent	X																																																						
Demographics, Medical History & Physical Exam	X																																																						
Pregnancy Test 	X																																																						
CEAP Classification	X																																																						
Physical Assessment of Limbs	X		X	X	X	X	X	X																																															

	Villalta Score, VCSS	X			X	X	X	X	X 	
	VEINES-QOL/Sym, EQ-5D QOL	X			X	X	X	X	X 	
	Procedure Data		X							X
	Serum Creatinine, CBC	X								
	INR (if on warfarin)	X			X	X	X	X	X	
	Document Adverse Events	X 	X	X	X	X	X	X	X	
	Document Device Deficiencies		X	X	X	X	X	X	X	
	Medication 	X	X	X	X	X	X	X	X	
	Discontinuation Information 			X	X	X	X	X	X	

 Pregnancy test for women of child-bearing potential only. Must be done within 7 days prior to the index procedure.

 Adverse Event assessment need to be done as of the moment the subject is enrolled in the study (i.e. subject signed and dated the informed consent form).

 Medication which will be collected: Antithrombotics, Antibiotics, Immunosuppressants, NSAIDs, Steroids, Diuretics, Calcium-channel blockers, Statins

 Assessments and questionnaires should be taken before any intervention.

 The discontinuation data is needed whenever the subject ends involvement in the study.

### Schedule of Imaging Assessments and Visit Windows

Data Collection Requirement	Screening/Baseline (<30 days)	Procedure		Hospital Discharge	30 Day (-7 days, +14 days)	6 Months (± 30 days)	12 Months (± 30 days)	24 & 36 Months (± 30 days)	Unscheduled visit for intervention in target vein
		Pre-stenting	Post-stenting						
Duplex Ultrasound	X			X 	X	X	X 	X	X
Venogram	1	X 	X				4		X
IVUS	1	X 	X						X
X-ray					3		X	X	X 

 Diagnosis can be made during the screening/baseline prior to the index procedure based on objective imaging using venography or IVUS. Diagnosis can also be made during the index procedure, prior to stenting. In case venogram and IVUS are not performed pre-stenting at the time of the index procedure, the pre-procedure venogram and IVUS should be sent to the core laboratory. If screening and pre-procedure venogram/IVUS are performed, then the pre-procedure venogram/IVUS should be sent to the

	
core laboratory. The DUS examination immediately after the index procedure needs to be performed between 0 and 7 calendar days from the index procedure. When the first examination after the procedure is non-diagnostic, a second examination has to be performed as soon as possible. Every effort should be made to perform this within 7 calendar days after the index procedure.
 
 X-rays at 30 days will be performed on the first 30 subjects only. They will be assessed for first safety analysis (i.e. stent fracture).
 
 An additional venogram must be performed when:
 
 
(1) DUS assessment is suggestive of <math>\geq 50\%</math> restenosis or occlusion per investigator assessment, or;
 
(2) when DUS is non-diagnostic or suboptimal such as when a subject is obese (e.g. with a BMI <math>> 40</math>), or;
 
(3) is clinically required, or in other words when the subject is having symptoms of venous disease in the target limb requiring a venogram.
 
 
 Plain x-ray is required pre and post re-intervention to assess for stent fracture.

--	---

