### 10.3.1 Demographics, Medical History & Physical Examination

A careful medical history and physical examination were to be taken prior to the implant procedure. For any interventions, the date of the most recent intervention was to be captured.

Data collected at baseline:

- Gender
- Age at time of enrollment
- Race/Ethnicity, to be collected per the FDA Guidance for Collection of Race and Ethnicity Data in Clinical Trials (2016), in support of regulatory submissions in the US (FDA).
- Risk factors, such as hypertension, diabetes, hyperlipidemia, tobacco use, obesity (BMI), previous knee/hip replacement, immobility and any other cardiovascular risk factors, with measure of severity and current treatment
- Co-existing cardiovascular conditions (including, but not limited to superficial ablation, congestive heart failure, peripheral vascular disease, previous myocardial infarction (MI))
- Symptoms
- Physical examination
- Assessment of target lesion and access vessel characteristics
- Medications: Antithrombotics, Antibiotics, Immunosuppressants, NSAIDs, Steroids, Diuretics, Calcium-channel blockers, Statins;

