## 10.12.6 Imaging

### 10.12.6.1 Venogram

A venogram (target limb) **must** be performed:

- during the index procedure, prior and post stent placement to aid with stent sizing and lesion assessment;
- in case a re-intervention in the target vein takes place;
- to assess the primary effectiveness performance goal endpoint during the 12 month follow-up visit only when:
  - (1) DUS assessment is suggestive of  $\geq 50\%$  restenosis or occlusion per investigator assessment,
  - (2) when DUS is non-diagnostic or suboptimal such as when a subject is obese (e.g. with a BMI $>40$ ), or
  - (3) clinically required, or in other words when the subject is having symptoms of venous disease in the target limb requiring a venogram.

Furthermore, a venogram (target limb) **may** be performed:

- during screening: the diagnosis can be made based on objective imaging using venography or IVUS;
- at all other time points, an additional venogram may be performed at the investigator discretion.

In case that the subject refuses a venogram, it will be documented in the eCRF. This is not considered a deviation.

All venographic imaging examinations should be performed according to the core laboratory guidelines and are analyzed by an independent core laboratory (See **Section 13.4**).

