#### 14.6 Handling of Dropouts and Missing Data

For those subjects not evaluable for primary effectiveness endpoint, multiple imputations will be carried out using the logistic regression approach for a dichotomous outcome using PROC MI in SAS for patients not experiencing the event and not having endpoint data for at least 330 days of follow-up.

The following variables will be included in the imputation model as covariates:

- Age
- Gender
- Race
- Ethnicity
- Diabetes
- Total occlusion
- Venous disease category
- Villalta score at baseline
- CEAP score at baseline
- VCSS class at baseline
- Reference vessel diameter
- Lesion length

If there are relatively few missing data points (e.g., <10%) for a given variable, a simple gender-specific imputation using the mean (for continuous variables) or median (for dichotomous or categorical variables) of the non-missing values will be done. If there are >10% missing data points, the variable will be excluded from the imputation analysis. Five data sets will be imputed from these covariates and will mimic different realizations of the missing data. For the endpoint, the numerator (the numerator is the point estimate of the treatment for the effectiveness endpoint) and its relevant standard error (the pooled standard error of

treatment for the effectiveness endpoint) will be pooled across the 5 data sets using established variance-adjustment methods (e.g., via PROC MIANALYZE in SAS) to create one overall numerator and denominator. The lower bound of the 97.5% pooled CI will be compared to the effectiveness PG.

The Tipping Point method will be adopted to further evaluate study primary objectives by assessing the impact of missing or unknown outcome data on study results. Tipping point analysis results for both primary effectiveness endpoint and primary safety endpoint will be reported.

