## 6.1 Performance Goal: Primary Effectiveness Endpoint

The primary effectiveness PG endpoint in this study is primary patency. The statistical hypothesis on this endpoint is that primary patency through 12 months will exceed a PG established from historical literature references using venous stenting as the treatment of choice. Formally, the null and alternative hypotheses to be tested appear below:

$$\begin{aligned}H_0: n &\leq PG \\H_A: n &> PG\end{aligned}$$

where  $n$  is the primary patency at 12 months in the study population and  $PG$  is the performance goal, which is calculated as follows. An extensive and independent review of the available literature produced references on venous stenting in similar patient populations. These data are derived from published studies of venous stenting which measured target vessel patency as an endpoint. To estimate the expected rate of primary patency in the study population at 12 months, the review of the available literature was used (see ABRE CIP Appendix A).

Based on the literature, the weighted mean expected primary patency was 85.7%. By subtracting a margin of indifference of 10% from expected performance ( $85.7\% - 10\% = 75.7\%$ ); consequently, the value of 75% is therefore taken as the  $PG$  for the current study. A margin of 10% has been commonly used for primary patency.

For analysis of the imaging component of primary patency, if a subject has both a valid venogram and DUS during the 12-month follow-up period then the venogram will be used. If no venogram is available, then the DUS will be used.

Further details regarding the analysis algorithm for primary patency are found in Appendix A.

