## 6.3 Sample Size Calculation

Primary Effectiveness: Using the assumptions above on the  $PG$  and anticipated outcome, we assume desired power of at least 92% under hypothesis testing relative to the performance goal at a one-sided alpha of 0.025. The resulting evaluable sample size required is then 160 subjects using exact binomial

test for a single proportion. Accounting for attrition during follow-up, the sample size is augmented by 20% to 200 subjects. Every effort will be made, however, to minimize loss to follow-up.

Primary Safety: Using the assumptions above on the performance goal and anticipated outcome, we assume desired power of at least 92% under hypothesis testing relative to the PG at a one-sided alpha of 0.025. The resulting evaluable sample size required is then 193 subjects using exact binomial test for a single proportion. Accounting for attrition during follow-up, the sample size is augmented by 3.5% to 200 subjects. Every effort will be made, however, to minimize loss to follow-up.

In summary, the overall power of the study is at least 84% while the effectiveness and safety PGs and the projected rates needed to achieve them are as follows:

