## 7.4 Handling of Missing, Unused, and Spurious Data and Dropouts

### 7.4.1 Multiple Imputation

For primary effectiveness endpoint, primary analysis will be performed using all evaluable data. Multiple imputation will be performed as sensitivity analysis to assess the robustness of the study data to the missing endpoints. For subjects not evaluable for primary effectiveness endpoint, the multiple imputation will be carried out using the logistic regression approach for a dichotomous outcome using PROC MI in SAS for subjects not experiencing the event and not having endpoint data for at least 330 days of follow up.

The following variables will be included in the multiple imputation model as covariates:

- Age
- Gender
- Race
- Ethnicity
- Diabetes
- Venous Disease category (aDVT vs. PTS vs. NIVL)
- Villalta score

- VCSS
- Reference Vessel Diameter
- Lesion length

If there are relatively few missing data points (<10%) for a given baseline variable, a simple gender-specific imputation using the mean (for continuous variables) or median (for dichotomous or categorical variables) of the non-missing values will be done. If there are >10% missing, the variable will be excluded from the imputation analysis. Five data sets will be imputed from these covariates and will mimic different realizations of the missing data. For the endpoint, the numerator (the numerator is the point estimate of the treatment for the effectiveness endpoint) and its relevant standard error (the pooled standard error of treatment for the effectiveness endpoint) will be pooled across the 5 data sets using established variance-adjustment methods (e.g., via PROC MIANALYZE in SAS) to create one overall numerator and denominator. The point estimate and the lower bound of the one-sided 97.5% pooled CI will be presented and compared to the primary analysis and the effectiveness PG

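### Baseline BMI is a foreseeable predictor of missing 12-month patency and is collected, but neither multiple-imputation covariate list includes it

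*Protocol*

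**What the plan says.** **Imaging.** Patency is read from duplex ultrasound (DUS). At 12 months a venogram is also required in three situations, one of them "when DUS is non-diagnostic or suboptimal such as when a subject is obese" (Protocol Synopsis imaging schedule; repeated in Protocol 6.3.1, Table 7, 10.9 and 10.12.6.1, and in SAP 7.9.1). BMI above 40 is the illustration given. Obesity is the only subject characteristic named as a reason for an unreadable scan.

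**Refusal.** Protocol 10.12.6.1: "In case that the subject refuses a venogram, it will be documented in the eCRF. This is not considered a deviation".

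**Baseline data.** Protocol 10.3.1 collects BMI as the measure of obesity, in the same risk-factor list as diabetes.

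**Imputation.** Protocol 14.6: "The following variables will be included in the imputation model as covariates". Its list is age, gender, race, ethnicity, diabetes, total occlusion, venous disease category, baseline Villalta, CEAP and VCSS, reference vessel diameter and lesion length. SAP 7.4.1: "The following variables will be included in the multiple imputation model as covariates". Its list is the same without total occlusion and CEAP. Diabetes is in both; BMI is in neither.

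**Role.** SAP 7.4.1 makes multiple imputation a sensitivity analysis and compares its lower bound with the 75% goal. The primary analysis uses evaluable subjects. SAP 7.4.2 adds a tipping-point analysis for both primary endpoints.

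**The concern.** Imputation corrects a complete-case estimate only as far as the model contains variables that predict both missingness and outcome. The plan itself points to one likely predictor of missingness: a subject with high BMI is more likely to have an unreadable duplex, and the back-up image depends on the subject accepting a venogram. If such subjects also lose patency more often than their other covariates suggest, a model without BMI fills in their outcomes largely from leaner subjects. The imputed rate then sits close to the evaluable-only rate, and the agreement looks like robustness when it partly reflects a shared bias.

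What is at stake is how far the sensitivity analysis can be trusted. The primary decision is not affected.

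**Working it through.** **1. The plan's own figure.** Inputs from SAP 6.1 and 6.3: goal 75%, expected patency 85.7%, N = 160, one-sided alpha 0.025, reject at 131 or more successes.
- P(X ≥ 131 | 160, 0.75) = 0.0247
- P(X ≥ 131 | 160, 0.857) = 0.9288
- 160 / (1 − 0.20) = 200

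All three match the plan. BMI enters none of them, so adding it changes none of them.

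**2. Scale.** One subject in 160 is 1/160 = 0.6 points. The exact one-sided 97.5% lower limit is 75.02% at 131/160 and 74.33% at 130/160. At the expected result (0.857 × 160 ≈ 137) it is 79.2%.

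**3. Possible bias.** The documents give no BMI distribution, no missingness by BMI and no patency by BMI, so these inputs are assumptions. Let q be the share of subjects with BMI above 40, m the proportion of them with missing 12-month patency, s their patency, and 85.7% the patency of the others. Overall missingness is held at 20%. The Protocol's 20% is its allowance for attrition; using it here as total missingness is a further assumption.

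The high-BMI share among evaluable subjects is q(1 − m)/0.80, so

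bias = [q − q(1 − m)/0.80] × (0.857 − s) = q(m − 0.20)/0.80 × (0.857 − s).

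| q | m | s | Bias, points |
|---|---|---|---|
| 5% | 30% | 85% | 0.00 |
| 5% | 50% | 75% | 0.20 |
| 10% | 30% | 75% | 0.13 |
| 10% | 50% | 75% | 0.40 |
| 20% | 50% | 75% | 0.80 |
| 10% | 70% | 65% | 1.29 |
| 20% | 70% | 65% | 2.59 |

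Middle case: 0.10 × 0.30/0.80 × 0.107 = 0.0040. True patency is 0.10 × 0.75 + 0.90 × 0.857 = 84.6%, and the evaluable-only rate is 85.0%.

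A broader definition of obesity gives a similar order. With 15% obese, missing 50% against 15% and patency 75% against 88%, the true rate is 86.05% and the evaluable-only rate 86.8% (+0.7). With 25% obese, missing 45% against 12% and patency 70% against 91%, the rates are 85.75% and 87.4% (+1.6).

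These are evaluable-only biases. They carry over in full to an imputation that is blind to BMI and to everything correlated with it. The listed covariates, diabetes and VCSS for example, may recover part of the gap, so each figure is an upper value for its own inputs.

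**4. Room in the model.** Expected failures among 160 evaluable subjects are 160 × 0.143 ≈ 23. The SAP list needs at least 11 coefficients: disease category has three levels, and race is counted as one. That is 23/11 ≈ 2.1 failures per coefficient. With BMI it is 23/12 ≈ 1.9; with BMI, total occlusion and CEAP as single terms, 23/14 ≈ 1.6.

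**5. Who reaches the imputation.** Evaluability clause (c) in Protocol 14.3 and SAP 7.1.3 and 7.9.1.2 asks for 330 days of follow-up without an event and names no image. SAP 10.3.2.2 ranks the qualifying images, but SAP Table 5 has no row for a subject with no 12-month image and no revascularization. A subject with an unreadable duplex, a refused venogram and 330 days of contact could be read as an evaluable success and would then never be imputed.

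**The case against.** Much of the opposing case stands.

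- A reader might infer that the plan treats obesity as making the duplex unreadable. It does not. Obesity is an example, and the plan's response is a required venogram. How often that is refused, and by whom, is not stated.
- A reader might infer that the imputed rate is biased. That needs a link between BMI and patency beyond the listed covariates, and no document gives one. The bias could be zero.
- A reader might infer that the effectiveness conclusion is at risk. Imputation is a sensitivity analysis, and at the expected 137/160 the lower limit clears the goal by about four points. Shifts of this size matter only within a few subjects of 131.
- The tipping-point analysis does not depend on the imputation covariates. For illustration, an exact limit on all 200 needs 163 successes. With 137 of 160 observed, 26 of the 40 missing would have to be patent. That analysis covers part of the worry. It shows how many failures would reverse the result, but SAP 7.4.2 gives no criterion for how many to expect, so it does not replace a well-specified imputation.
- The SAP history records that the covariate lists were updated in version 3.0, and Protocol section 14 describes methods set at the start of the study. Dropping total occlusion and CEAP may have been deliberate, and no bias from it is shown. The two current texts still differ, no reason is given, and the Protocol dated March 2021 keeps the longer list.
- The premarket analysis is complete and the remaining phase is descriptive, so a change now is post hoc. That argues for labelling it as such.

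**Conclusion.** The concern holds as a modest, inexpensive improvement to a sensitivity analysis. The documents establish that high BMI is a foreseeable predictor of missing 12-month patency, that it is collected, and that both imputation lists omit it. They do not establish that it predicts patency, so the effect is conditional: about 0 to 2.6 points of overstatement over the assumed ranges (5–20% of subjects with BMI above 40, 30–70% of them missing, patency 65–85% in them against 85.7% in others, 20% missing overall), with a middle case of 0.4, less than one subject in 160. The mismatch between the two lists and the silence of clause (c) on imaging can be read directly from the text and need no assumption.

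**What to change.** 1. Add baseline BMI as one continuous term to the covariates in SAP 7.4.1 and Protocol 14.6. If the 12-month analysis is already done, report this as a labelled supplementary run beside the planned imputation.
2. Reconcile the lists: restore total occlusion and CEAP in SAP 7.4.1, or state why they were removed.
3. State that evaluability as a success under clause (c) requires a diagnostic 12-month image, and send subjects without one (and without an event) to the imputation. Without this, adding BMI may not reach the subjects it is meant for.

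Cost: wording changes and one rerun, with no new data collection. The statistical cost is strain on a logistic model with about 23 expected failures, so keep BMI to a single term, check for separation, and justify each restored covariate.
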